#### Study Completion:

For each subject in the study, the end of study will be reached when the 60-day treatment **and** post-treatment safety follow-up period at 180 days since enrollment have been completed.

### **Subject withdrawal:**

A subject may be withdrawn from the study prior to that subject completing all of the study related procedures. Some reasons may include:

- Subject safety issues
- Failure of subject to adhere to protocol requirements
- Disease progression
- Subject decision to withdraw from the study (withdrawal of consent)

Withdrawn subjects may not reenter the study.

### **Premature withdrawal from study:**

Subjects may voluntarily withdraw from the study for any reason at any time. Subjects are considered withdrawn if they state an intention to withdraw further participation in all components of the study, die, or are lost to follow-up for any other reason. The investigator may withdraw a subject from the study (without regard to the subject's consent) if they believe that continued participation in the study would be contrary to the best interests of the patient.

Subjects are considered as lost to follow-up if all reasonable attempts by the investigator to communicate with the individual fail. The investigator will take preventive measures to avoid a subject being lost to follow-up (*e.g.*, document different ways of contact such as telephone number, home address, e-mail address, person to be contacted in case the subject cannot be reached). If the subject cannot be reached, the investigator will make a reasonable effort to contact the subject, document all attempts and enter the loss of follow-up information into the Case Report Form (CRF). The following methods will be used: at least two telephone calls will be placed to the last available telephone number (each call on different days) and one registered letter will be sent by post to the last available home address. If the subject is still unreachable after all contact attempts listed above, he/she will be lost to follow-up.

If premature withdrawal occurs for any reason, the reason for premature withdrawal from the study, along with who made the decision (subject, investigator) will be recorded in the CRF.

### **Subject replacement:**

Subjects withdrawn from the study will be replaced by newly recruited subjects meeting inclusion criteria matching similar baseline characteristics (age, gender, race, , and/or blood or urine assay senescence marker positivity).

#### **4.4.2 Data Collection and Follow-up for Withdrawn Subjects**

For safety monitoring, telephone contact of withdrawn subjects receiving Fisetin will be attempted. Research data will not be collected on subjects after they are withdrawn from the study, any additional evaluation will be for subject safety only.

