### 4.4 Early Withdrawal of Subjects

#### 4.4.1 When and How to Withdraw Subjects

All subjects will be assessed during the 2 days of medication administration, subsequent days of medication administration, and all study visits. If a severe adverse event (SAE) occurs at any time during administration of the 2-day drug regimen, a formal review will occur, and subsequent patients will be enrolled one at a time using the same regimen. If three or more events accrue, the pilot study will be held and either a potential dosing regimen revisited, or discontinuation of the study protocol will occur. Other interventions will be at the direction of the Food and Drug Administration and Mayo Institutional Review Board.

Patients may also wish to withdraw if they perceive that their symptoms of carpal tunnel syndrome are not improving, and they wish additional treatment such as surgery or a steroid injection. If they are tolerating the Fisetin otherwise, we will request that they continue the Fisetin in addition to the other treatments, and such patients will continue to be followed, but will be excluded from the final analysis. We aim to continue enrollment until 40 patients complete the 60-day trial time point without intervening treatment for their CTS.

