## **6.8 Visit 6, Day 180 (remote visit) (±14 days)**

At day 180, subjects will be contacted by phone and email. The study coordinator will assess the subject for Adverse Events, and record answers to the hand/wrist pain VAS, hand/wrist interference VAS, the BCTQ questionnaire, changes to medical history, and concomitant drugs into REDCap. Alternately, the subject can answer the hand/wrist pain VAS, hand/wrist interference VAS, the BCTQ questionnaire directly through the links sent via email.

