#### Handling of Missing Data

Basic summaries of subject demographics and baseline BCTQ will be run for subjects who drop out prior to completion of the study *vs.* those who completed the 60-day portion of the study.

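### Subjects the investigator withdraws before Day 60, including for undefined disease progression, have no Day 60 BCTQ and are replaced, which can tilt the single-arm mean change towards improvement

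*Combined protocol and SAP*

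**What the plan says.** The rule comes from several sections read together.

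- **Withdrawal (4.4.1, Subject withdrawal).** "A subject may be withdrawn from the study prior to that subject completing all of the study related procedures". The listed reasons include safety, non-adherence and "Disease progression", which is not defined. The paragraph on premature withdrawal adds that the investigator may withdraw a subject without the subject's agreement.
- **Data after withdrawal (4.4.2).** "Research data will not be collected on subjects after they are withdrawn from the study". Any later contact is for safety only. Table 1 has no early-termination assessment.
- **Replacement (4.4.1, Subject replacement).** "Subjects withdrawn from the study will be replaced by newly recruited subjects meeting inclusion criteria matching similar baseline characteristics".
- **Other CTS treatment (4.4.1).** Subjects who are not improving and take an injection or surgery are handled differently: "such patients will continue to be followed, but will be excluded from the final analysis". Enrolment aims for 40 subjects who reach Day 60 without such treatment.
- **Analysis (7.2, 7.3).** The main population is Day 60 completers. The analysis is a confidence interval and paired t-test for the change. A mixed model on all BCTQ measurements is secondary.
- **Missing data (7.2).** "Basic summaries of subject demographics and baseline BCTQ will be run for subjects who drop out" before completing the study, compared with those who completed the 60-day portion. No other method is given under that heading.
- **Remote completion (6.8).** At Day 180 the subject can answer "the BCTQ questionnaire directly through the links sent via email". Section 6.7 describes Day 60 as an in-person visit and mentions no link.

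**The concern.** Progression of CTS is the primary outcome seen from the unfavourable side. A subject withdrawn for it before Day 60 is likely to have a poor change score, and that score is not collected. The replacement is matched on baseline characteristics, which restores the number of subjects but not the lost outcome. With no control arm, no comparator carries the same loss, so it enters the mean change directly. Comparing baseline data between dropouts and completers cannot show that the dropouts did worse after dosing.

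Section 1.1 makes a Phase 3 study depend on showing, among other things, that symptoms are reduced, and sets no numerical threshold there. A modest upward shift could therefore affect that decision.

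**Working it through.** **1. The plan's own figure.** Section 7.1 gives n = 40, SD of change 0.7, significance level 0.05 and a paired t-test. Sidedness is not stated. Solving the noncentral t with 39 degrees of freedom, two-sided, gives a minimum detectable change of 0.318 at 80% power and 0.368 at 90%. These round to the stated 0.3/0.4. One-sided values (0.280/0.330) round to 0.3/0.3 and do not match, so two-sided 0.05 is used below. The sample size stands; the issue is bias, not power.

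**2. Bias from replaced withdrawals.** Count improvement as positive. Assumptions:

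- 40 completers are analysed, and k further dosed subjects were withdrawn before Day 60 and replaced;
- the true mean change over all 40 + k dosed subjects is zero;
- the k subjects would have averaged d points worse than the completers;
- the completers' SD is 0.7.

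The documents give neither k nor d, so both are shown as ranges. If m is the completer mean, then 40m + k(m − d) = 0, so m = d × k/(40 + k).

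Example: k = 8, d = 0.7 gives 0.7 × 8/48 = 0.12.

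**3. Chance of a falsely significant improvement.** The noncentrality is m/(0.7/√40) = m/0.1107, and the critical value is t(0.975, 39) = 2.023. For the example, 0.1167/0.1107 = 1.05, and the upper-tail probability is 18%.

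| k | withdrawn, k/(40 + k) | bias, d = 0.7 | bias, d = 1.0 | false improvement, d = 0.7 | false improvement, d = 1.0 |
|---|---|---|---|---|---|
| 0 | 0% | 0 | 0 | 2.5% | 2.5% |
| 1 | 2% | 0.02 | 0.02 | 3.5% | 4% |
| 2 | 5% | 0.03 | 0.05 | 5% | 6% |
| 4 | 9% | 0.06 | 0.09 | 8% | 12% |
| 8 | 17% | 0.12 | 0.17 | 18% | 31% |
| 12 | 23% | 0.16 | 0.23 | 30% | 53% |

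**4. Scale.** The half-width of the 95% interval is 2.023 × 0.1107 = 0.22. The largest bias in the table, 0.23, is about that size, and is under a quarter of the 1-point target.

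**5. Check with other selection models** (true mean zero, SD 0.7, 40 completers).

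- Removing and replacing the worst 5%, 10%, 20% or 30% of subjects gives a completer mean of +0.08, +0.14, +0.25 or +0.35, and a false improvement in about 10%, 28%, 83% or over 99% of trials. This is an extreme form of selection.
- Withdrawing at random 10%, 25% or 50% of those who worsen gives +0.03, +0.08 or +0.19, and about 4%, 11% or 41%. Subjects who worsened still make up 47%, 43% and 33% of the completers.

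The direction is the same in every case. The size depends on how many are withdrawn and how closely withdrawal follows the outcome.

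**The case against.** A reader might infer that subjects who worsen never reach the primary endpoint. The documents do not support that. Withdrawal is permissive, and progression is one possible reason. A subject who worsens and stays without injection or surgery has a Day 60 BCTQ and is analysed. In the second check above, worseners vanish from the completers only if all of them are withdrawn. Nor is the endpoint lost for every withdrawn subject, because follow-up runs to Day 180 and a withdrawal after Day 60 leaves the primary value in place.

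A reader might also infer that the protocol equates stopping drug with leaving the study. It does not do so generally. The individual stopping rule in 8.5 and the pregnancy rule in 8.4 stop the drug without stating study withdrawal, and 4.4.1 keeps following subjects who take other CTS treatment. For subjects who leave all components, die or are lost, little could be collected in any case. The avoidable gap is withdrawal decided by the investigator before Day 60.

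The data are also not wholly beyond repair. The BCTQ is taken at Day 29, the mixed model could use those scores, 7.3 promises summaries of subjects who do not reach Day 60, and the reason for withdrawal and who decided it are recorded. These help only in part. The mixed model is secondary and the text does not say that non-completers enter it, a subject withdrawn before Day 29 may have no post-dose score, and no Day 60 value exists for any of them.

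Finally, the size rests on assumed counts and deficits. Withdrawals for safety or non-adherence need not be worse at all, and with one or two withdrawals the effect is slight. Section 7.2 puts the focus on the confidence interval and hypothesises a 1-point change. All of this stands and limits the severity. It does not remove the direction of the bias when withdrawal is linked to outcome.

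**Conclusion.** The concern holds for subjects withdrawn by the investigator before Day 60. Their Day 60 BCTQ is not collected, they are replaced, and the completer analysis has neither a control arm nor a planned method that addresses their missing outcomes. Where such withdrawals are related to outcome, the mean change shifts towards improvement.

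On the stated assumptions (40 completers, SD 0.7, no true change, withdrawn subjects 0.7 to 1.0 worse), the bias is 0.02-0.05 for one or two withdrawals, 0.06-0.09 for four, 0.12-0.17 for eight and 0.16-0.23 for twelve. The chance of a falsely significant improvement rises from 2.5% to 3.5-6%, 8-12%, 18-31% and 30-53%. That is enough to distort a test or interval against zero. It could not by itself produce a 1-point improvement. This should be fixed, but it does not invalidate the design.

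**What to change.** **Section 4.4.2.** State that a subject withdrawn by the investigator before Day 60 for progression, non-adherence or safety stays in outcome follow-up unless consent is withdrawn. Collect the Day 60 and Day 180 BCTQ and VAS scores, using the emailed REDCap link of 6.8 when the subject cannot attend. This leaves the rules for stopping study drug unchanged.

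**Section 7.2.**

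- Report the Day 60 change in all dosed subjects with a Day 60 BCTQ beside the completer result, and show subjects who had an injection or surgery separately, because their scores also reflect that treatment.
- State that the mixed model uses the BCTQ scores of all dosed subjects, including Day 29 scores of non-completers.

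**Cost.** Protocol and consent wording and a few more questionnaires; the link already exists. The estimate may be less favourable. Subjects who refuse all participation, die or are lost will still be missing, and their number and reasons should be reported with the result. A Day 60 score that was not collected cannot be recovered at analysis, so the change helps only subjects who have not yet passed that visit.

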## **5 Study Drug**

### **5.1 Description**

While Fisetin is currently available and marketed as a dietary supplement, this study will use a product manufactured under cGMP conditions. The Fisetin will be supplied in 100 mg capsules

to be administered orally. The investigational supplies will be obtained from Vital Nutrients or Sharp Clinical Services, contracted GMP manufacturers. Fisetin capsules manufactured by Vital Nutrients are 00 opaque blue in color, Fisetin capsules manufactured by Sharp Clinical Services are size 00 green in color.

## **5.2 Treatment Regimen**

The treatment dosing regimen is based on the preclinical information available about Fisetin along with information about similar clinical drug trials using the alternative senolytic compounds Dasatinib and Quercetin. Participants will be administered Fisetin over a two-day course of treatment twice during the study duration. Each day subjects will receive a target dose of 20 mg/kg of body weight. Therefore, for an adult with a body weight of 75 kg, each day the participant will take 15 of the 100 mg capsules. Dosing should be completed in as short of a time as possible, with a goal of 10 minutes and a maximum time of 60 minutes to complete ingestion of the capsules. Subjects can empty the capsules into room temperature or cold drinks or puddings, such as milk, yoghourt, or apple sauce, if they are unable or unwilling to ingest multiple capsules. The drink or pudding will be consumed within 10 to 60 minutes. By mass spectrometry, we verified that Fisetin is stable under these conditions. Dosing will occur at days 0 and 1 and repeated at days 29 and 30.

## **5.3 Preparation and Administration of Study Drug**

The request for the study drug will be sent to the research pharmacy and individually prepared for each subject. The number of capsules will be calculated for each study subject based on body weight to meet the target dose each day of approximately 20 mg/kg of body weight. Study subjects will be instructed to ingest all of the capsules from one bottle each day.

## **5.4 Subject Compliance Monitoring**

Patient adherence to study treatment will be monitored by requiring the subjects to attend in-person visits (Days 0 and 29), where they will be provided the study drug.

The CTRU nurse will document drug administration on day 0 and 29 in the subject's chart as well as in the Subject Drug Diary. The Subject Drug Diary will document compliance for day 1 and 30 of drug administration at the subject's home.

## **5.5 Prior and Concomitant Therapy**

Subjects may continue all treatments except for two related to CTS: steroid injection or surgery, during the first 60 days of the study. If a study participant is required to initiate any medication listed in Appendix 1 of the Investigator Brochure during the study, the PI will reassess their continued participation in the study.

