## **6.7 Visit 5, Day 60 (±5 days)**

At the 60-day visit, subjects will return to Mayo Clinic's Clinical Trial Research Unit (CTRU). Subjects will have their vital signs measured and review changes to their medical history and concomitant medications with the CTRU nurse. Women of childbearing potential will confirm their pregnancy status via a point of care pregnancy test. The subject will provide a blood and urine sample for inflammation and senescence markers as well as safety labs. The study team will administer the hand examination and record the information into REDCAP. The subject will fill out hand/wrist pain VAS and hand/wrist interference VAS assessments and the Boston CTS (BCTQ) questionnaire in REDCap. The study team will record adverse events and collect the Subject Drug Diary.

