### **6.9.2 Medical History/Prior and Concomitant Medications**

Medical history will be obtained preliminarily from subject medical records with incomplete entries to be completed during the screening visit by subject recall. At subsequent visits, the CTRU nurse will record medical history and concomitant medications. Medication history will include current medications only. The subject will also be questioned on their tobacco and caffeine usage.

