### 6.9.11 Interaction Compliance

All participants will be questioned regarding their alcohol and caffeine usage and will record their compliance to reduce their consumption, if needed, based on the study protocol.

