### Individual Subject Stopping Rules

Any subject who experiences a SAE of any sort, or who is found to meet, after enrollment, any exclusion criterion, will no longer receive the study drug.

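### After the Day 30 dose, the visible protocol neither asks subjects to avoid off-study fisetin or flavonoid supplements nor asks about use since the last contact, so six-month maintenance could not be credited to the two study courses alone (minor)

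*Combined protocol and SAP*

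**What the plan says.** **Restriction.** Section 4.2.4 excludes anyone currently taking a flavonoid supplement. It allows flavonoid-rich food because the amounts are far below the trial dose. Table 1 re-checks eligibility at Day 0 and Day 29 and not afterwards. Under the individual stopping rules in 8.5, a subject found after enrollment to meet "any exclusion criterion, will no longer receive the study drug". The last study dose is on Day 30 (5.2).

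**Concomitant treatment.** Section 5.5: "Subjects may continue all treatments except for two related to CTS: steroid injection or surgery, during the first 60 days of the study". It adds that the investigator will reassess participation if a subject has to start a medication on the Investigator Brochure list.

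**Data capture.** At Day 60 (6.7) subjects "review changes to their medical history and concomitant medications with the CTRU nurse". At Day 180 (6.8) the coordinator enters "changes to medical history, and concomitant drugs into REDCap". Section 6.9.2 governs both: "Medication history will include current medications only". That section also asks about tobacco and caffeine, and 6.9.11 says "All participants will be questioned regarding their alcohol and caffeine usage". Neither names supplements.

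**Use of Day 180.** Section 3.5 lists the 180-day symptom outcome as a secondary endpoint. Section 7.2 makes persistence of the two-month BCTQ change at six months the second secondary hypothesis.

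**The concern.** Section 5.1 notes that fisetin is marketed as a dietary supplement. The trial has one open arm, so every subject knows what was given, and one who improved could buy the same compound. The protocol treats supplement use as incompatible with entry, but it does not visibly carry that view into the 150 days between the last dose and Day 180.

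At stake is the meaning of the six-month result. If repeat dosing helps and some subjects repeat it, a sustained BCTQ change would partly reflect the extra courses. There is no control arm to show this, and use that nobody recorded cannot be recovered at analysis.

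**Working it through.** **1. Does any visible provision cover supplements between Day 30 and Day 180?**

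| Provision | What it does | Why it leaves the gap |
|---|---|---|
| 4.2.4, flavonoid exclusion | Bars enrollment | Last re-checked at Day 29 (Table 1) |
| 8.5, individual stopping rule | Stops study drug | No effect once the Day 30 dose is taken |
| 5.5, first sentence | Rules out injection and surgery to Day 60 | Speaks of continuing treatments, not of starting a supplement |
| 4.2.4 and 5.5, Brochure list | Investigator reassesses | List not visible; concerns medications a subject has to start; neither a bar nor a look-back |
| 4.4.1, "Failure of subject to adhere to protocol requirements" | Permits withdrawal | No visible supplement requirement to breach after Day 30 |
| 4.4.1, "complete the 60-day trial time point without intervening treatment for their CTS" | Sets the enrollment aim | Ends at Day 60 |

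None of these asks a subject to avoid supplements up to Day 180.

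**2. Would use be recorded?** Ongoing daily use could be, since it is current at the contact. A completed course depends on how the contact is run. The visit text speaks of changes, which may prompt a look-back; 6.9.2 points the other way.

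The strictest reading can be illustrated. Assume a single 2-day course, starting on a random day from Day 61 to Day 180, and count it as current only if taken on the contact day. The eligible start days number 180 − 60 = 120, and only starts on Days 179 and 180 qualify: 2/120 = 1.7%. This shows what the rule does when read literally. It does not estimate what staff would miss in practice.

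**3. How large could the effect be?** The plan gives no figure on this point. Its nearest input is the SD of 0.7 for a 3-month BCTQ subscore change (7.1). With n = 40 and a two-sided paired t-test at 0.05, that SD gives a minimum detectable change of 0.318 at 80% and 0.368 at 90% power, matching the stated 0.3/0.4. Carrying the SD to the 4 months from Day 60 to Day 180 is an assumption. The 95% confidence half-width is then

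t(0.975, 39) × 0.7/√40 = 2.023 × 0.1107 = 0.224.

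Let p be the share who self-dose, f the share of the symptom loss they avoid, and L the true mean loss from Day 60 to Day 180. The loss masked is p × f × L. The documents give none of the three, so the values below are assumed, with f = 1 as the extreme:

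| L | p = 5% | p = 30% |
|---|---|---|
| 0.3 | 0.05 × 0.3 = 0.015 | 0.30 × 0.3 = 0.09 |
| 1.0 (the whole hypothesized gain) | 0.05 × 1.0 = 0.05 | 0.30 × 1.0 = 0.30 |

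With a 0.3-point loss, the masked part is well inside the half-width. With a 1.0-point loss and 30% self-dosing it exceeds the half-width, but 1.0 − 0.30 = 0.70 points of loss would still be visible. If fisetin has no effect, f = 0 and nothing is masked.

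**The case against.** The strongest reply is that the visit text is broader than 6.9.2. Reviewing changes at Days 60 and 180 naturally means looking back to the last contact, and a subject on a monthly regimen might well report it as current between doses. This stands in part. A reader might infer that nearly all off-study use would be missed, but the documents do not support that. They show only that no one is required to ask and that one rule points away from asking.

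A second reply is that the instruction may exist elsewhere. The Investigator Brochure is not supplied and the consent pages were removed. That is fair, and the point is limited to the visible protocol. A Brochure listing would still trigger reassessment only.

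A third is that adverse events are sought by specific questioning (8.2), and that 8.1 counts as non-serious events changes in clinical status that would make a subject meet an exclusion criterion. Buying a supplement is not obviously a change in clinical status, and the clause is not a look-back on supplement use.

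Finally, Table 1 labels Day 180 as post-study follow-up, and 5.5 leaves injection and surgery open after Day 60, which may matter more. Both are correct. But 3.5 and 7.2 still use Day 180 for a stated endpoint and hypothesis, so the fix should cover those treatments too.

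**Conclusion.** The point holds as a minor one, confined to the six-month maintenance hypothesis. After Day 30 the visible protocol neither asks subjects to avoid off-study fisetin or flavonoid supplements nor requires a question about use since the last contact, and the current-only rule could miss a completed short course. Maintenance at six months therefore could not be attributed to the two study courses alone.

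The frequency and effect of self-dosing are unknown and probably small; the calculation above only bounds them under assumed values.

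Two stronger readings are not supported. A reader might infer that the Day 60 primary result is compromised. But supplement eligibility is re-checked at Day 29, the remaining interval is about a month, medications are reviewed at Day 60, and the aim of no intervening treatment runs to that visit. A reader might also want a figure for the lost chance of detecting relapse. The plan specifies no Day 60 to Day 180 test and gives no self-dosing rate, so any such figure would rest on invention.

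**What to change.** 1. **Section 5.5:** ask subjects not to take non-study fisetin or flavonoid supplements through Day 180.
2. **Section 6.9.2 and Table 1:** at Days 60 and 180, replace the current-only rule with a dated question about any such supplement use since the last contact. At Day 180, also ask about any steroid injection or carpal tunnel surgery.
3. **Section 7.2:** report the number of users and the Day 180 BCTQ change with and without them, as a description only.

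The cost is one extra question at two existing contacts, one sentence in 5.5 and one summary. No visits, exclusions or subjects are added. Self-report will be incomplete. Dropping users may select on response, since those who improved, or those who relapsed, may be the ones who self-dose; the two summaries should be read together and neither treated as the corrected result.

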### **3.4 Primary Study Endpoints**

In this pilot study, our primary endpoint will be a decrease in CTS symptoms at 60 days (2 months) compared to baseline, as measured by the Boston CTS questionnaire.

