### 7.3 Subject Population(s) for Analysis

As a pilot study, all subjects who complete the 60-day study visit ( $60 \pm 5$  days) will be the main population of interest, though summaries will be made of those who do not reach that point.

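### The bar on steroid injection and surgery ends at 60 days, the primary BCTQ may be taken up to Day 65, and sections 4.4.1 and 7.3 disagree on a subject treated in between

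*Combined protocol and SAP*

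**What the plan says.** Section 5.5 (Prior and Concomitant Therapy) lets other treatment continue "except for two related to CTS: steroid injection or surgery, during the first 60 days of the study". The period is a number of days. It is not tied to Visit 5, and 5.5 does not say on which day the count starts.

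Section 3.4 sets the outcome: "our primary endpoint will be a decrease in CTS symptoms at 60 days (2 months) compared to baseline", measured by the BCTQ. Section 6.7 and Table 1 place that questionnaire at Visit 5, Day 60 with a window of 5 days either side. Section 6.9.5 adds that the answers describe the study hand as it is when the questionnaire is completed.

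Two sections decide whose score is analysed:

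- Section 7.3 takes as its main population "all subjects who complete the 60-day study visit", with the same ±5 day window. It does not mention other treatment for CTS.
- Section 4.4.1 deals with patients who feel no better and want surgery or an injection: "such patients will continue to be followed, but will be excluded from the final analysis". It then sets the enrolment target as 40 patients who "complete the 60-day trial time point without intervening treatment for their CTS".

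**The concern.** The restriction ends on a day count, while the primary assessment ends at a visit that may come later. No section joins the two. Full compliance with 5.5 can therefore still produce a primary score taken after an injection or operation. This is different from rescue treatment inside the restricted period, where 5.5 is breached.

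Either way of handling such a subject can favour fisetin. If the score is kept, any relief from the other treatment enters the before-after change, and a single-arm trial has no control group in which to see it. If the subject is excluded, the person lost is probably one who had not improved, since 4.4.1 itself describes those seeking injection or surgery in that way, and enrolment continues until an untreated completer takes the place. Because 4.4.1 and 7.3 differ, the choice could be made after the data are seen.

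**Working it through.** **Inputs.** Bar: 60 days (5.5). Visit 5 window: 60 ±5 days (6.7, Table 1, 7.3). N = 40, SD of change 0.7, desired difference 1.0, paired t-test at 0.05 (7.1). Days are counted from Day 0, and Day 60 is taken as the last barred day.

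**1. The plan's own figure.** Section 7.1 states a minimum detectable change of 0.3/0.4 at 80%/90% power. Noncentral-t power for a two-sided paired t-test with n = 40 and SD 0.7 gives 0.318 and 0.368, which round to 0.3/0.4. The figure reproduces, and this point does not affect it.

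**2. The gap in days.** Visit 5 may fall from 60 − 5 = Day 55 to 60 + 5 = Day 65. The days after the bar but still in window are 61, 62, 63, 64 and 65, so the gap is up to 5 days.

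**3. How many visits could be late.** The documents do not give the spread of visits. If they fell evenly over the 11 days of the window, 5/11 × 40 = 18.2, or about 18 of 40, would come after Day 60. This counts late visits, not treated subjects.

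**4. One subject traced through the text.** Suppose an injection on Day 61 and a BCTQ on Day 64.

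- Section 5.5: no rule broken.
- Section 6.7 and Table 1: visit in window.
- Section 7.3 read alone: score included.
- Section 4.4.1 read naturally: subject excluded and enrolment continues. If its time point means calendar Day 60, the subject had reached it untreated and counts toward the 40.

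**5. Size if the score is kept.** Shift in the mean = k × e / 40, for k treated subjects each gaining e points from the other treatment. Neither k nor e is in the documents, so these values are illustrations.

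- k = 1, e = 1.0 (set equal to the target): 1.0/40 = 0.025.
- k = 2 to 4, e = 1.0: 0.05 to 0.10.
- k = 1 to 4, e = 0.5 to 1.5: 0.0125 to 0.15.

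**6. Size if the subject is replaced.** Suppose the untreated change would have been 0 and the replacement shows the target change of 1.0. The shift is again (1.0 − 0)/40 = 0.025 per subject, so the two routes are of the same order.

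**7. Yardsticks.** Standard error = 0.7/√40 = 0.111. The 95% CI half-width = 2.023 × 0.111 = 0.22. The target is 1.0.

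**The case against.** The strongest reply is that the analysis is already protected. The exclusion sentence in 4.4.1 has no Day 60 cut-off, and its enrolment target asks for completers with no other CTS treatment on the way, which reads most naturally as up to the assessment. On that reading the Day 61 injection is excluded. This stands in large part. A reader might infer that relief from an injection will be credited to fisetin, but that requires following 7.3 alone or reading 4.4.1 narrowly. It does not remove the point: 7.3, the section that defines the analysis population, does not carry the exclusion. Applying the exclusion has its own cost, because it drops a subject who complied with 5.5 and was probably not improving.

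A reader might also infer that the 60 days run from consent, which can be up to 14 days before Day 0, so that the gap is much longer and could reach everyone. The documents do not support this. The visit schedule is numbered from Day 0, participation is given as 180 days with the last visit at Day 180, and adverse event reporting starts at Day 0. What stands is only that 5.5 should name its starting day.

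The size can be challenged too. Under the even spread, the gap days average (1 + 2 + 3 + 4 + 5)/5 = 3 per late visit. Two to four treated subjects would be 11% to 22% of the 18 late visits. Nothing in the documents shows that patients wait for the bar to end or that treatment clusters on Days 61 to 65. Nor do the documents give a time course for either treatment, so neither a full 1.0-point gain within 5 days nor the direction of an early change after surgery is established. All of this stands, and it is why the figures above are illustrations only.

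**Conclusion.** The mismatch is real. A subject can follow 5.5 fully, be treated on Days 61 to 65, and then give an in-window primary score that 7.3 keeps and that 4.4.1, read naturally, excludes. The gap is up to 5 days.

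The effect is probably small. At 0.025 per subject, two to four subjects move the mean by 0.05 to 0.10. That is below one standard error (0.111) and 5% to 10% of the 1.0-point target, though not negligible beside a CI half-width of 0.22 in a plan whose section 7.2 puts the emphasis on confidence intervals. The result rests on an assumed number treated and an assumed 1.0-point difference per subject. The sample size and power statement is unaffected. The figure of about 18 of 40 should be read only as the number of late visits under an even spread.

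The point is worth correcting because the repair is cheap and removes a choice that could otherwise be made after the data are seen.

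**What to change.** 1. Reconcile 5.5, 4.4.1, 6.7 and 7.3 so that the restriction period, the 60-day time point and the primary assessment refer to the same event on the same day count, with the starting day named. How long the two treatments are restricted is for the sponsor to decide.
2. State that when a subject is to have an injection or surgery before Visit 5, the primary BCTQ is collected beforehand, within the 60 ±5 day window. The emailed REDCap link that section 6.8 already uses at Day 180 can serve. State that this score counts as the Visit 5 BCTQ.
3. Make 7.3 carry the same handling of intervening treatment as 4.4.1, so that one rule decides who is in the primary analysis.

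The cost is a few sentences. The downside is that a few primary BCTQs are completed remotely or a few days early. The link covers the questionnaire only: the Visit 5 blood and urine samples and hand examination would still follow the treatment unless the visit itself is brought forward within its window. Sample size does not change.
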